11.6.3 Secondary outcome analysis

We will report the number of participants consented, screened, randomised and completing the trial as per trial workflow (Fig. 3).

We will estimate:

- Difference between the Hearing Intervention and the Healthy Intervention arms, in the proportion of participants maintaining hearing aid use, defined as a minimum of 4h a day on average since last trial assessment (when at home and in usual health) as established by data-logging at 6 months (end of trial), based on the hearing aid with the highest average use (as each participant has two hearing aids). Self-reported hearing aid use may also be employed if needed, for instance if no data-logging is available for a participant, as further specified in the Statistical Analysis Plan.
- Percentage of participants rating the interventions (Hearing Intervention and Healthy Ageing Intervention) as acceptable (ratings 3-5 on a 5-point Likert scale) based on Likert scale scores.
- Mean, proportions, differences in means and proportions across treatment arms with corresponding 95% confidence intervals will be calculated as appropriate for the cognitive scales and other trial outcomes, to inform the sample size calculation for a full scale trial.

We will produce appropriate summary estimates and report the following:

- Number of potential participants referred to the study researchers, screening visits scheduled and completed.
- Feasibility of the schedule of assessments, which will include proportion of completed interviews and completion rates of instruments and questionnaires, as well as relevant biometric data.
- Completion rates of the interventions by recording the proportion of participants who completed the intervention, any refused or discontinued visits for the Hearing Intervention and Healthy Ageing Intervention, and any refused or discontinued tests and instruments from the schedule of assessments.
- For the Hearing Intervention, we will record the number of participants with hearing aid fitted within 3 months (target: 80%) and reported side effects.
- Average hearing aid daily use measured as number of hours of use on average over 7 days (when at home and in usual health) as established by data-logging at 6 months (end of trial) for the Hearing Intervention and Healthy Ageing Arms. Self-reported hearing aid use may also be employed if needed, for instance if no data-logging is available for a participant, as further specified in the Statistical Analysis Plan.
- Number of unscheduled contact with participants, including type of contact (face to face or other) and whether this was with RA or research audiologist.
- Number of hearing aids lost by participants in the intervention and control arm.
- ROC analysis of HearCheck and Shoebox audiometry relative to gold standard full audiometric testing conducted by the trial audiologist, on the detection of hearing loss as defined for this trial (four-frequency pure tone average (0.5, 1, 2, 4 kHz) in the better-hearing ear of ≥ 25 decibels Hearing Level (dB HL) and <70 dB HL or a pure tone audiometric threshold at 4 KHz in the better ear of ≥ 30 decibels dB HL).

We will also report

- Reported side effects.

A detailed statistical analysis plan will be written prior to database lock.

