Trial design and methods:	
For TACT, participants with hearing loss and MCI will be randomised to a hearing intervention (home-based provision of hearing aids, and adherence support delivered over a 6 week intervention) or a healthy ageing intervention (home-based educational intervention, to match intensity of social contact). Participants will be assessed on their hearing, quality of life, physical activity, mood, social interactions, and daily function at baseline and 6 months.
 
During the COVID-19 pandemic, the RHI sub-study will be a single-arm, non-randomised trial in patients with MCI and hearing loss, who will receive a remotely delivered hearing intervention over 4 weeks.

Trial duration per participant:	6 months for intervention delivery and follow-up in TACT. The RHI sub-study during COVID-19 pandemic will last 4 weeks per participant.
Estimated total trial duration:	24 months
Planned trial sites:	Single-site
Total number of participants planned:	76 for TACT During the COVID-19 pandemic, we aim to recruit 12 participants to RHI sub-study.
Main inclusion/exclusion criteria:	Participants will be 55 years of age or older, with a diagnosis of MCI, and with mild to moderate adult-onset hearing loss, community-dwelling, without any self-reported hearing aid use in the past month.

For the single-arm Remote Hearing Intervention sub-study during the COVID-19 pandemic, we will invite those participants that had been consented for the randomised trial prior to the onset of COVID-19 who either (a) completed the healthy ageing intervention and are not using hearing aids; or (b) were included in the trial but could not complete their allocated intervention due to the onset of COVID-19.

Statistical methodology and analysis:

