The anticipated fully-sized trial will be powered to identify differences in cognitive decline between those allocated to an interventional arm of supported hearing aid use versus a healthy ageing intervention in the MCI population. The current project will perform preparatory work for this future full-sized trial addressing the difficulties that this future trial faces to be successful. The definitions of pilot and feasibility randomised studies used in this document are as per CONSORT statement [11].

Addressing the challenges raised by COVID-19 Pandemic

COVID-19 is a grave global challenge for public health. It is also a challenge for clinical trials, especially those relying on face-to-face delivery of interventions, such as TACT. This has been recognised by

funders and regulatory agencies. In the following we have followed recent guidance on how to restart trials safely ^{1,2}.

For TACT, the main challenge is ensuring the safety of participants. Participants are aged 55 and over, so they are at higher risk from COVID-19 complications; some of our participants are in the high-risk category and shielding. The initial home-based hearing aid and support intervention would therefore not be suitable as it could put participants at increased risk of contracting the virus. This is a challenge also faced by NHS audiological cases, which have been paused during the epidemic except for urgent audiological treatment. Hearing aid provision and support is not an urgent treatment. However, given that in the absence of a vaccine social distancing for vulnerable populations may be maintained for months or years, it is important that Remote Hearing Interventions for audiological care are developed and tested, with a view to potential dementia prevention in the MCI population. Effective hearing aid treatment is likely to be particularly important during the pandemic as the measures in place to prevent the spread of the virus, such as social distancing and face coverings or masks, will have a disproportionate detrimental impact in those people with impaired hearing, who often rely on lip reading for communication. We will therefore test the feasibility and acceptability of a Remote Hearing Intervention during the COVID-19 pandemic.

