8.1 Pre-intervention assessments

Screening visit (Visit 0, day 0)

The screening visit will be conducted by an audiologist (Aud) and research assistant (RA).

The following trial procedures will be conducted at the screening visit (Visit 0):

- Consent of participant, and, if applicable, of communication partner (RA)
- Assessment of non-audiological eligibility criteria: confirm that criteria are met with regards to age, English command, willingness to be randomised and comply with trial procedures (RA)
- If the participant is eligible, then administration of hearing screening: Hearcheck and Shoebox audiometry (RA)
- Measurement of ambient noise (sound level meter), with remedial measures taken if ambient noise greater than 50 A-weighted decibel dB(A) (Aud)
- Interview and assessment by research audiologist, audiological medical history, visual inspection, otoscopy, tympanometry, pure tone audiometry (air conduction (with Audiocups), bone conduction & masking), tuning fork test (if required), phoneme recognition in quiet, speech in noise (QuickSIN); to assess audiological eligibility criteria (Aud)
- if individual meets all the inclusion criteria, inclusive of audiometric eligibility criteria, as per section 6.1 and 6.2: randomisation (Aud)

- if randomised to hearing intervention: evaluation of optimal hearing aid type (based on audiometric test results, physical appearance of outer ear, and manual dexterity); decision on earmold or receiver-in-canal (RIC). If earmold then take impression at end of visit (Aud)
- if hearing loss is detected, the research audiologist will inform the participant's GP of the results of the hearing test

The screening visit can be administered over two sessions on different days if required. The assessment will be timed by the RA, as one of the objectives of the trial is to assess tolerability of the schedule of assessments, with 2 hours considered the maximum tolerable for frail older adults. If the assessment goes beyond two hours, or if the participant requests a break or is showing signs of fatigue in the opinion of the researcher, the researcher will offer scheduling another meeting within 2 weeks to finalise the testing.

Baseline visit (Visit 1)

The baseline visit will be conducted by an RA.

Purpose: to gather baseline measures of primary and secondary outcomes.

When: Day 0 to 2 weeks after screening (V0) and 1-2 weeks before first intervention visit (V2).

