11.3 Sample size calculation

This pilot trial will assess the feasibility of proceeding to the future definitive RCT of sufficient duration to detect differences in cognitive changes between arms. The main feasibility questions that the pilot aims to answer are: (a) is the trial feasible, in the sense of resulting in sufficiently high recruitment, randomisation and sufficiently low dropout at 6 months; (b) is the Hearing Intervention deliverable and acceptable to participants; (c) estimate the difference in hearing aid use at 6 months between the Hearing Intervention and Healthy Ageing Intervention arms to inform sample size estimates for the future trial. We are including cognitive outcomes to assess their feasibility and acceptability, and to provide estimates including standard deviation to be used in the sample size calculation for the full trial. As a feasibility study, the current trial is not powered to detect differences in the cognitive outcomes between the arms. Therefore, only descriptive analyses will be performed using the data collected. No formal power calculation is necessary, and instead the sample size has been determined as to provide sufficient precision (sufficiently narrow confidence intervals) for trial estimates of recruitment and randomisation, dropout, acceptability of the intervention, and difference in hearing aid usage between arms, as detailed below.

With 76 randomised participants, we will achieve the following 95% confidence intervals (CI) for our expected estimates of recruitment, randomisation, dropout, acceptability of the intervention, and difference in hearing aid adherence between the Hearing Intervention and Healthy Ageing Intervention at the end of trial [88]:

1. Recruitment and randomisation of eligible participants with a MCI diagnosis from NHS community memory clinics. Target: 50% of eligible participants will be randomised; with n=76 recruited subjects the 95% CI would be [39-61].
2. Follow-up: target of 80% randomised participants with complete follow-up at 6 months,

95%CI with n=76 would be [71-89].

3. Acceptability of the Hearing Intervention: proportion of participants allocated to the Hearing Intervention completing ≥ 2 intervention sessions – expected value $\geq 80\%$ of intervention group, 95% CI with n=76 would be [71-89].

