4. Difference in daily hearing aid adherence between arms: target of 50% difference between the Hearing Intervention and Healthy Ageing Intervention arms in the proportions of participants maintaining hearing aid use at 6 months (end of follow-up), 95% CI with n=76 would be [31-69].

Mean, proportions, differences in means and proportions with corresponding 95% confidence intervals will be calculated as appropriate for the cognitive scales and other trial outcomes, to inform the sample size calculation for a full scale trial.

Criteria for the decision of progression to the main trial

We judge that these confidence intervals provide acceptable ranges to inform continuation to the main trial. The final decision to “go” or “stop”, that is, whether to proceed or not to the main trial, will be taken by the Trial Steering Committee after the end of trial and with consideration of whether the trial has met its primary and secondary outcomes, as well as any lessons learnt during the pilot.

As a **guidance to this decision**, we anticipate that if the 4 endpoint estimates above in this section, as measured in the pilot trial, fall within their respective expected confidence intervals as detailed above, this will be a “go” signal for a full scale trial. If the endpoint estimates fall up to 10% below the lower limit of their target confidence interval (as detailed above in this section) we will consider whether modifications to the trial design to improve these endpoints would be sufficient to remediate these issues when proceeding to the main trail. If any of these endpoints fall below these minimal rates this will be a “do not progress to RCT” signal.

The Remote Hearing Intervention sub-study (COVID-19) will contribute to this decision by providing initial descriptive data and a qualitative assessment on the feasibility and acceptability of a remote version of the Hearing Intervention.

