11.6 Statistical analysis

11.6.1 Summary of baseline data and flow of participants

List of variables to be used to assess baseline comparability of the randomised groups using means (SD) and counts (proportions) as appropriate:

- Age
- Sex
- Cognition scale: Addenbrooke Cognitive Examination (ACE-III) score
- Quality of life: SF36, EQ-5D
- Function: 4-item Lawton-Brody IADL
- Social activities: SFDEM, UCLA loneliness
- Frailty: grip strength
- Physical activity: as measured by accelerometry at baseline
- Geriatric Depression Score
- Self-reported hearing disability - Hearing Handicap Inventory for the Elderly – Screening version (HHIE-S)
- Phoneme Recognition in Quiet score (baseline)
- Hearing Threshold PTA average (0.5-4 KHz)

We will produce a consort flow diagram (<http://www.consort-statement.org/>) to illustrate the flow of participants in the trial, based on draft (presented as Fig 3).

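### For outcomes measured at baseline and 6 months, the protocol names only means, SDs and differences in means, which is an incomplete input for sizing a full trial on cognitive decline

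*Protocol*

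**What the plan says.** Section 11.3 gives two reasons for collecting the cognitive measures. One is to learn whether they are feasible and acceptable. The other reads: "to provide estimates including standard deviation to be used in the sample size calculation for the full trial". It says the pilot is not powered for cognition and concludes: "Therefore, only descriptive analyses will be performed using the data collected". It then names the outputs: "Mean, proportions, differences in means and proportions with corresponding 95% confidence intervals will be calculated as appropriate for the cognitive scales and other trial outcomes". Section 11.6.3 repeats this for the comparison of arms: "Mean, proportions, differences in means and proportions across treatment arms with corresponding 95% confidence intervals will be calculated as appropriate for the cognitive scales".

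Section 3 gives the target of the later trial: "The anticipated fully-sized trial will be powered to identify differences in cognitive decline".

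The baseline visit (V1, Section 8.1) has this aim: "Purpose: to gather baseline measures of primary and secondary outcomes". Sections 8.1 and 8.4 and Appendix 1 show ACE-III, DWRT, TMT, HHIE-S, SF-36, EQ-5D, IADL, SF-DEM, UCLA Loneliness and grip strength at both V1 and V6. In the analysis section, baseline values appear in Section 11.6.1, under "List of variables to be used to assess baseline comparability of the randomised groups". That table includes ACE-III but not DWRT or TMT. Section 11.6 does not bring the V1 score into the estimate of the arm difference.

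**The concern.** Decline is change from baseline, so the variance that governs a trial of decline depends on how strongly the follow-up score correlates with the baseline score. The SD at one time point does not carry that information. A planner who takes from the pilot report only what Sections 11.3 and 11.6.3 list would have an SD and a difference in means, but not the quantity that converts the SD into the variance of a baseline-adjusted comparison.

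Two things are at stake. The full trial could be sized too large if it adjusts for baseline and the SD is used alone. The pilot's own interval for each arm difference would also be wider than the same data allow, and would carry any chance baseline imbalance, which is more likely in a small sample.

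**Working it through.** **Inputs.** 76 randomised 1:1, so 38 per arm (Section 5). Retention target 80% (Section 11.3): 0.80 × 76 = 60.8, about 61. Complete data for 36 participants before COVID-19 (Section 2), taken here as 18 per arm. The correlation ρ between V1 and V6 is not given, so it is assumed at 0.3, 0.5 and 0.7.

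**The plan's own figures.** Section 11.3 states intervals for proportions only. With p ± 1.96√(p(1−p)/76), 50% gives 38.8 to 61.2 and 80% gives 71.0 to 89.0. For 70% against 20% with 38 per arm, 50 ± 100 × 1.96√((0.21 + 0.16)/38) gives 30.7 to 69.3. These match the stated [39-61], [71-89] and [31-69]. No SD, correlation or interval width is stated for a continuous outcome.

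**Effect on full-trial size.** Required N is proportional to the variance of the analysed quantity. Adjusting for baseline multiplies the outcome variance by 1−ρ², so sizing on the unadjusted SD overstates N by 1/(1−ρ²):

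- ρ = 0.3: 1/0.91 = 1.10; residual SD √0.91 = 0.95 of the SD
- ρ = 0.5: 1/0.75 = 1.33; residual SD 0.87 of the SD
- ρ = 0.7: 1/0.51 = 1.96; residual SD 0.71 of the SD

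If the full trial used a change score instead, the variance factor would be 2(1−ρ) = 1.4, 1.0 and 0.6. The SD alone would then undersize the trial below ρ = 0.5 and oversize it above. Either way, ρ is the missing quantity.

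**Effect on the pilot's interval.** Half-widths are in units of the outcome SD, with n = N/2 per arm.

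Unadjusted: t(N−2) × √(2/n). At N = 36: 2.032 × √(2/18) = 0.677.

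Adjusted: t(N−3) × √(2/n) × √(1−ρ²) × √(1 + 1/(N−4)). At N = 36 and ρ = 0.5: 2.0345 × 0.3333 × 0.8660 × 1.0155 = 0.596.

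| N | Unadjusted | ρ = 0.3 | ρ = 0.5 | ρ = 0.7 |
|---|---|---|---|---|
| 36 | 0.677 | 0.657 | 0.596 | 0.492 |
| 61 | 0.512 | 0.493 | 0.448 | 0.369 |
| 76 | 0.457 | 0.439 | 0.399 | 0.329 |

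At ρ = 0 the adjusted interval is slightly wider (0.689 against 0.677 at N = 36).

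**How well the pilot can estimate ρ.** With 36 pairs and an observed ρ of 0.7, the Fisher 95% interval is tanh(0.867 ± 1.96/√33), or 0.48 to 0.84. Then 1−ρ² runs from 0.77 to 0.30, about a 2.5-fold range in required N.

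**The case against.** The strongest reply is that model form belongs in the statistical analysis plan, which Section 11.6.3 says will be written before database lock. The protocol never uses the words raw or unadjusted. It qualifies the outputs as appropriate to the outcome, and its mention of the SD is not an exhaustive list. A baseline-adjusted difference is still a difference in means, so adjustment is not ruled out.

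Much of this stands. A reader might infer that the protocol commits to raw comparisons, but the text does not say so; it only names no adjustment. The reply does not dispose of the point, though. Section 11.6.3 expressly leaves the handling of self-reported hearing aid use to the SAP, whereas for the cognitive scales it names the estimator itself. The qualifier most naturally chooses between means and proportions.

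A reader might also infer that the planned SD is wrong or oversized. It is not. It is a standard input that misleads only if the full trial adjusts for baseline and nobody applies 1−ρ². The paired data are collected, so ρ can be computed later.

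Nor does the precision of a cognitive difference bear on the pilot's own decisions. The analysis is descriptive, the intervals justifying 76 participants are all for proportions, and so are the four progression endpoints.

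Finally, writing the 6-month residual SD into Section 11.3 as a fixed input would carry its own risk. Section 5 envisages a full trial of 2 to 3 years. If the correlation is lower over that interval, a 6-month residual SD would undersize the trial. This limits the remedy.

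**Conclusion.** The point holds as an improvement of low severity. For continuous outcomes taken at V1 and V6, the named outputs are incomplete for the purpose Section 11.3 gives them. The possible overstatement of full-trial size is 1.10 to 1.96 times for ρ from 0.3 to 0.7. It depends on two conditions the protocol does not settle: that the full trial adjusts for baseline, and that the SD is used without the correlation. At 36 completers, split equally, adjustment would shorten the half-width from about 0.68 SD to 0.60 (ρ 0.5) or 0.49 (ρ 0.7). At ρ = 0.3 the gain is small. Every figure here rests on an assumed ρ. The documents do not support a claim that a stated number, the sample size of 76 or a progression criterion is wrong on this ground.

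**What to change.** In Section 11.6.3, or in the SAP, state that for each continuous outcome measured at both V1 and V6 the arm difference and its 95% CI come from a linear model of the V6 score on arm and V1 score. Keep the unadjusted difference as a secondary line. Report the V1 to V6 correlation with its CI, and the residual SD, beside the unadjusted SD.

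In Section 11.3, list the correlation and residual SD with the SD as information for the full-trial sample size, not as fixed inputs. Add that a 6-month correlation is imprecise at this sample size and may be lower over 2 to 3 years, so the full-trial calculation should use a range.

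The cost is one extra parameter per model and a little more reporting. No new data are needed, and the analysis remains descriptive.

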11.6.4 Sensitivity and other planned analyses

Qualitative analysis

- Qualitative assessment of interventions: We will interview participants and relatives about each intervention (involvement, practicality, acceptability) and about their opinion of the assessment until theoretical saturation is achieved (which we anticipate will be reached with 12-16 participants per intervention arm). We will include both participants who have benefited from the intervention and those for whom it was not useful, to find out what helped and what could be better.

12 Record keeping and archiving

At the end of the trial, all essential documentation will be archived securely by the CI for a minimum of 20 years from the declaration of end of trial.

Essential documents are those which enable both the conduct of the trial and the quality of the data produced to be evaluated and show whether the site complied with all applicable regulatory requirements.

The Sponsor will notify sites when trial documentation can be archived. All archived documents must continue to be available for inspection by appropriate authorities upon request.

13 Oversight Committees

